9.5 STUDY SIZE

In a previous study, 205.426 (*clinicaltrials.gov NCT 00699699*): “Assessment of Physical Activity (PF10 Sub Domain of SF-36 Activity Score) and Tolerability in COPD Patients During Treatment With Spiriva® Respimat®), with over 1000 patients treated with Spiriva® Respimat®, therapeutic success (i.e., 10-point increase in the PF-10 score between visit 1 and visit 2) was achieved in 61% of the patients.

In this study, a lower therapeutic success rate is expected as patients may be already on maintenance treatment at baseline. Assuming a 50% therapeutic success rate and 900 patients, the 95% confidence interval for the therapeutic success rate would be between 46.7% (lower limit) and 53.3% (upper limit) (*level of accuracy of ± 3.3%*), basing the calculations on a binomial distribution.

To account for a 10% drop-out rate, the sample size is adjusted to 1.000 patients.

Calculations were performed with the PASS software package, version 2011.

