9. RESEARCH METHODS

9.1 STUDY DESIGN

This is an observational study as the medicinal product is prescribed according the normal clinical practice. The patient's assignment to a particular therapeutic strategy is not decided in advance by the study protocol but it will be determined by routine clinical practice and the decision to prescribe a particular medicinal product will be clearly dissociated from the decision to include the patient in the study. No other clinical intervention (diagnostic or clinical follow up) than the usual clinical practice will be applicable in the study.

This is a self-controlled study design enrolling consented COPD patients who will be treated with Spiolto® Respimat® according to the approved SmPC.

Patients will be enrolled consecutively and will be followed over an observational period of approx. 6 weeks.

Every physician is invited to enroll the first consecutive patients he/she chooses to treat with Spiolto® Respimat®. The decision to treat will be taken independently of participation in this NIS and will be made before participation is considered.

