9.2 SETTING

9.2.1 Study sites

It is planned that data of approximately 1.000 patients from approximately 200 sites (primary care sites) in Spain will be collected. Site selection will be performed to reflect routine COPD care in order to secure representativeness of the COPD population. The inclusion of five patients is planned per investigator.

A log of all patients included into the study (i.e. having given informed consent) will be maintained in the Investigator Site File (ISF) irrespective of whether they have been treated or not.

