9.9 LIMITATIONS OF THE RESEARCH METHODS

The intention of this NIS is to collect new data on the physical functioning and exercise capacity of COPD patients on treatment with Spiolto® Respimat® in a real world setting.

A NIS is the most suitable instrument for obtaining information about the use of medicines in everyday therapeutic practice and thus for investigating prospectively questions in everyday therapeutic practice.

Consecutive enrolment will be employed to minimize selection bias. The entry criteria are non-restrictive which will permit the enrolment of a broad patient population. The choice of treatment is at the discretion of the investigator.

There are a number of different types of bias that could influence the data collection and analysis, such as selection, information, and channeling bias.

Selection bias could occur at the site level and the patient level. To minimize the site level selection bias, the goal is to have participating centers that have access to all available treatment options which are approved for use in that country for the targeted COPD patients. To minimize selection bias at the patient level, consecutive enrolment is performed. Information bias will be minimized by the use of standard eCRF, questionnaire and physicians' training on the study protocol.

An additional limitation is that the physical functioning questionnaire (PF-10) is only assessing 10 items of the full 36-Item Short Form Health Survey (SF-36).

The 7-item satisfaction scale, which is to be completed by the patient in order to measure satisfaction with Spiolto® Respimat® use, is a self-designed Boehringer-Ingelheim scale, without a public source or validation status.

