9.10.2 Study records

Case Report Forms (CRFs) for individual patients will be provided by the sponsor via remote data capture. All of the clinical data and site/investigator characteristics will be captured via a web-based Electronic Data Capturing system. The site staff will enter and edit the data via a secure network, with secure access features (username, password and secure identification – an electronic password system). A complete electronic audit trail will be maintained.

Patients must not be identified on the eCRF by name. Appropriately coded identification (i.e. Patient numbers) must be used. All patient questionnaires will be paper-based and will be left at the site upon completion by the patient.

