4.2. RATIONALE FOR SAMPLE SIZE

In a previous study, 205.426 (clinicaltrials.gov NCT 00699699: "Assessment of Physical Activity (PF10 Sub Domain of SF-36 Activity Score) and Tolerability in COPD Patients During Treatment With Spiriva® Respimat®"), with more than 1000 patients treated with Spiriva® Respimat®, therapeutic success (i.e., 10-point increase in the PF-10 score between visit 1 and visit 2) was achieved in 61% of patients.

In this study, a lower therapeutic success rate is expected, as patients may already be on maintenance treatment at the start. Assuming a therapeutic success rate of 50% and 900 patients, the 95% confidence interval for the therapeutic success rate would be between 46.7% (lower limit) and 53.3% (upper limit) (level of accuracy of $\pm 3.3\%$), basing the calculations on a normal approximation to the binomial distribution.

Taking into account a possible drop-out rate of 10%, the sample size is adjusted to 1000 patients.

Calculations were made using the PASS software package, version 2011.

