5.2.3. Analysis of primary endpoint

For the primary endpoint, the proportion of patients with therapeutic success at visit 2 i.e., approximately 6 weeks (define as 10-point increase in the PF-10 score between visit 1 and visit 2) together with the 95% confidence interval will be presented.

***PF-10** is a sub-domain of SF-36 and consists of 10 items evaluating the scope of the restrictions experienced when carrying out routine activities. Each PF-10 item may be answered with “yes, limited a lot”, “yes, limited a little”, or “no, not limited at all”, with a score of 1, 2 or 3. The scores of the 10 items are added up, resulting in a value between 10 (a patient who answers all questions with “yes, limited a lot”) and 30 (a patient who answers all questions with “no, not limited at all”). The final sum of the individual scores will be standardised to a range of 0 to 100 using the following formula: $100 \times (\text{sum} - 10) / 20$.¹

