6.4.1. Analysis of primary endpoint

This section will describe the frequency and percentage of "Therapeutic success" at visit 2 (defined as: 10-point increase in the PF-10 score between the baseline visit (visit 1) and the visit after 6 weeks (visit 2) will be presented together with the 95% confidence interval.

Table 21. Therapeutic success after 6 weeks (visit 2) – Full Analysis Set (FAS)		
	Total n (%)	CI (95%)
Therapeutic success¹ n (%)		
Therapeutically successful		
Not therapeutically successful		

Therapeutic success: 10-point increase in the PF-10 score between visit 1 and visit 2.

¹ Of the total number of patients who have PF-10 data at the baseline visit (visit 1) and at the visit after 6 weeks (visit 2)

Figure 4. Therapeutic success after 6 weeks (visit 2) – Full Analysis Set (FAS)
[pie chart]

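### The ±3.3-point precision and the primary 95% CI take no account of about five patients per investigator at about 200 sites, and no CI method is named

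*Protocol*

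**What the plan says.** **Planned precision.** Protocol 9.5 assumes 50% success in 900 patients, so that "the 95% confidence interval for the therapeutic success rate would be between 46.7% (lower limit) and 53.3% (upper limit"), and inflates to 1000 for 10% drop-out. The protocol describes the basis as binomial. SAP 4.2 repeats the figures, "basing the calculations on a normal approximation to the binomial distribution".

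**Recruitment.** Protocol 9.2.1 and SAP 4 plan about 1000 patients from about 200 primary care sites: "The inclusion of five patients is planned per investigator". Under Protocol 9.1, "Every physician is invited to enroll the first consecutive patients he/she chooses to treat" with the product.

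**Primary analysis.** SAP 5.2.3 and 5.2.7 say that the success proportion "together with the 95% confidence interval will be presented". SAP 6.4.1 says that it "will be presented together with the 95% confidence interval". Protocol 9.7.1 is no more specific. The normal approximation in SAP 4.2 describes only the sample-size calculation. Protocol 9.3.3 lists no covariates, and neither document uses site in the study size or in the primary interval.

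**Status of the analysis.** Protocol 9.7.1 and SAP 5.2.7 call the analyses descriptive and the confidence intervals exploratory.

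**The concern.** Patients of one physician may resemble each other in outcome. They share that physician's threshold for prescribing the product, the inhaler training given at the site, the way the paper questionnaires are handed out, and the local timing of a visit fixed only at approximately six weeks. Any of these could make success positively correlated within site. The documents do not show that such correlation exists, but they give no reason to take it as zero.

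If it exists, 900 patients carry less information than 900 independent ones, and an ordinary binomial 95% CI covers the true rate less often than 95% of the time. The success rate with its interval is the only primary result, and precision is the only basis for the study size, so coverage is the property that matters here. With no method named, the decision to use or ignore site would be made at the analysis stage.

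**Working it through.** **Inputs from the documents:** success rate p = 0.50, evaluable n = 900, 10% drop-out (Protocol 9.5, SAP 4.2); about 200 sites and five patients per investigator (Protocol 9.2.1, SAP 4). **Assumed:** ICC of 0.01 to 0.10, because the documents give none.

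**1. Reproduce the plan's figure.** Half-width = 1.96 × √(p(1−p)/n) = 1.96 × √(0.25/900) = 3.27 points, giving 46.73% to 53.27%. Wilson gives 46.74% to 53.26% and Clopper-Pearson 46.68% to 53.32%. Enrolment: 900/(1 − 0.10) = 1000. The printed figures are correct under independence, and the choice among ordinary binomial methods hardly matters at this n.

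**2. Add clustering.** Evaluable patients per site: m = 900/200 = 4.5. Design effect: DE = 1 + (m − 1) × ICC = 1 + 3.5 × ICC. Effective n = 900/DE. Half-width = 3.267 × √DE. Coverage of the unadjusted interval = 2Φ(1.96/√DE) − 1.

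| Assumed ICC | DE | Effective n | Half-width (points) | Coverage of unadjusted 95% CI |
|---|---|---|---|---|
| 0 | 1.000 | 900 | ±3.27 | 95.0% |
| 0.01 | 1.035 | 870 | ±3.32 | 94.6% |
| 0.05 | 1.175 | 766 | ±3.54 | 92.9% |
| 0.10 | 1.350 | 667 | ±3.80 | 90.8% |

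With m = 5 instead of 4.5, ICC 0.10 gives DE = 1.40 and ±3.87. Unequal recruitment across sites would raise DE somewhat.

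**3. How far the printed ±3.3 survives.** It still rounds to 3.3 while the half-width is below 3.35: DE = (3.35/3.267)² ≈ 1.052, so ICC ≈ 0.052/3.5 ≈ 0.015.

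**4. Does a site-clustered interval work with about 200 clusters?** Simulation with 20,000 runs, beta-binomial outcomes, 200 sites of five, 10% random loss and a true rate of 50%. The clustered interval uses a linearised variance and t with (sites − 1) degrees of freedom.

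| ICC | Coverage, ordinary Wald | Coverage, site-clustered | Mean half-width, site-clustered |
|---|---|---|---|
| 0 | 94.8% | 94.9% | ±3.28 |
| 0.01 | 94.5% | 94.9% | ±3.34 |
| 0.05 | 92.6% | 94.9% | ±3.57 |
| 0.10 | 90.5% | 94.7% | ±3.83 |

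At ICC 0 the ordinary interval has a mean half-width of ±3.26, so clustering costs about 0.02 points when there is nothing to correct.

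**The case against.** Nothing printed is miscalculated, and the assumptions behind ±3.3 are stated. The harm rests wholly on an ICC that the documents do not supply, and several features point to a small one. The PF-10 is completed by the patient. The outcome is a within-patient change, which removes stable differences in level between sites. Enrolment is of the first consecutive patients, with the decision to treat made before participation is considered. The remark in Protocol 9.9 that "Selection bias could occur at the site level and the patient level" concerns which centres and patients take part; that is representativeness, which a clustered CI does not repair. A 50% rate is also the worst case for width: at the earlier study's 61%, 1.96 × √(0.61 × 0.39/900) = 3.19 points, and ±3.3 would survive rounding up to a DE of about 1.10 (ICC about 0.03). The analysis is descriptive, with no threshold or comparator.

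All of this stands as a limit on the size of the problem. The missing CI method, taken alone, is only missing detail. But none of these points makes the ICC zero, and a success rate away from 50% narrows the interval without restoring its coverage. A site-clustered interval would settle the question from the data.

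**Conclusion.** The point holds. The ±3.3 points assume independent patients in a design that recruits them in groups of about five, and the method for the primary CI is left open. Over the assumed ICC range of 0.01 to 0.10, with 4.5 evaluable patients per site, the half-width is ±3.3 to ±3.8 points, and an ordinary binomial interval covers about 94.6% to 90.8%. If there is no within-site correlation, the stated precision stands. The point estimate is unaffected, and no test or decision rule changes. This is a modest, conditional weakness in the interval for the only primary result. It should be corrected because the correction costs so little. Confidence is medium, since the true ICC is unknown.

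**What to change.** - **SAP 5.2.3 and 5.2.7:** state that the 95% CI for therapeutic success is computed with site as the cluster, for example by SAS PROC SURVEYFREQ with a CLUSTER statement, or by an intercept-only GEE by site with robust standard errors.
- **SAP 4.2:** add that ±3.3 points holds under independence and would be about ±3.3 to ±3.8 for an assumed ICC of 0.01 to 0.10 with 4.5 evaluable patients per site.

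**Cost:** a few lines of SAP text and one procedure call in software already specified. Protocol 9.10.2 says "All of the clinical data and site/investigator characteristics will be captured via a web-based Electronic Data Capturing system", so no new data are needed. Enrolment, the point estimate and the protocol text stay as they are. The only downside is a possibly slightly wider interval.

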9.6 DATA MANAGEMENT

A data management plan (DMP) will be created to describe all functions, processes, and specifications for data collection, cleaning and validation. The electronic Case Report Forms (eCRFs) will include programmable edits to obtain immediate feedback if data are missing (also negative answers, unknown), out of range, illogical or potentially erroneous. These rules may encompass simple checks such as range validation or presence/absence of data. Concurrent manual data review may be performed based on parameters dictated by the DMP. Ad hoc queries to the sites may be generated and followed up for resolution. A source data quality audit may be initiated to ensure that the data in the database is accurate.

The database will be housed in a physically and logically secure computer system maintained in accordance with a written security policy. The system will meet the standards of the International Committee on Harmonization guideline E6R1 regarding electronic study data handling. Patient confidentiality will be strictly maintained.

9.7 DATA ANALYSIS

9.7.1 Main analysis

In this non-interventional study, cross-sectional data at study baseline and longitudinal follow-up data over 6 weeks will be collected for patients with chronic obstructive pulmonary disease (COPD) requiring long-acting dual bronchodilation in routine clinical practice.

Baseline data will be described using a cross-sectional approach. Data from the longitudinal follow-up will be summarized descriptively. Due to the nature of this non-interventional study, there is no (confirmatory) hypothesis testing foreseen in a strict statistical sense. Analyses are descriptive in nature and confidence intervals and p-values from statistical models are used for exploratory purposes. No adjustments for multiple testing are made in the evaluation of statistical significance. Consequently, significant differences may be observed by chance alone and p-values should be interpreted as exploratory and with caution.

Details will be described in the statistical epidemiological analysis plan (SAP).

No formal hypothesis testing will be performed since this is a self-controlled study.

All patients who have received at least one dose of Spiolto® Respimat® will be included in the analysis; this is the treated set. All analyses will be performed on the treated set (as-treated analysis). If patients have missing values for an outcome, those patients will be excluded for that outcome's analysis.

The assessment will be carried out using SAS® software, 9.4 version or later. The statistical characteristics presented in the end-of-text tables will be N / mean / SD / min / median / max

for continuous variables. Tabulations of relative and absolute frequencies will be presented for categorical variables. Incidence rates and 95% CI will be given when appropriate.

The analyses will relate to the following data as recorded in the eCRF:

- Patient demographics (age, gender, height, and weight);
- Comorbidities;
- COPD related and other concomitant medication
- History of smoking
- Reported exacerbations
- Breathlessness based on mMRC score at visit 1
- Physical Functioning based on PF-10 scores (therapeutic success at visit 2); primary outcome
- Changes from visit 1 to visit 2 in the PF-10 score; secondary outcome
- Patient satisfaction with Spiolto® Respimat® at visit 2 only; secondary outcome
- General condition of the patient: evaluated by the physician (Physician's Global Evaluation (PGE)); secondary outcome
- Adverse Drug Reactions (ADR & SADR), fatal AEs, pregnancies
- GOLD spirometric classification (1,2, 3, 4)
- GOLD patient groups (A, B, C, D)
- Details of treatment with inhaled respiratory agents before the study
- Details of treatment with respiratory agents during the study
- Reasons for ending treatment during the observation period
- Details of treatment continuation / discontinuation

For the primary outcome, the proportion of patients with therapeutic success will be presented together with the 95% confidence interval.

The safety data will be reported according to local requirements. Statistical analysis and reporting of AEs will be descriptive in nature. Occurrences of AEs will be analyzed relative to the number of patients treated. The following parameters will be included in the safety analyses:

- Adverse events (AEs) and serious adverse events (SAEs)
- Adverse drug reactions (ADRs), serious and non-serious

If less than half of the PF-10 questions are missing for a patient, the missing values will be replaced with the mean of the other values and the PF-10 score will be calculated. If half or more than half of the PF-10 questions are missing, no score will be calculated and the PF-10 score will be marked as missing. No other missing data will be imputed. Every effort will be made to collect complete data at the specified time points. Any removal from the analysis will be documented, stating the site and patient number as well as the reason for removal.

9.8 QUALITY CONTROL

To improve and secure data quality, automatic data checks upon data entry will be done within the eCRF. In the eCRF, plausible ranges of values for numeric data entries as well as logical data entries and listings will be provided for each entry field. Based on this, checks on completeness and plausibility will be performed upon data entry in the eCRF.

Validity of data entry thus is ensured by integrated validation checks performed by the system, indicating missing or implausible entries to the document list or investigator. All corrections will be visible from the systems audit trail.

No regular source data verification is planned in this study. However, in case of decreasing compliance (i.e. of missing data, data discrepancies, protocol violations, etc.) a for-cause audit or risk-based monitoring visit will be performed.

9.9 LIMITATIONS OF THE RESEARCH METHODS

The intention of this NIS is to collect new data on the physical functioning and exercise capacity of COPD patients on treatment with Spiolto® Respimat® in a real world setting.

A NIS is the most suitable instrument for obtaining information about the use of medicines in everyday therapeutic practice and thus for investigating prospectively questions in everyday therapeutic practice.

Consecutive enrolment will be employed to minimize selection bias. The entry criteria are non-restrictive which will permit the enrolment of a broad patient population. The choice of treatment is at the discretion of the investigator.

There are a number of different types of bias that could influence the data collection and analysis, such as selection, information, and channeling bias.

Selection bias could occur at the site level and the patient level. To minimize the site level selection bias, the goal is to have participating centers that have access to all available treatment options which are approved for use in that country for the targeted COPD patients. To minimize selection bias at the patient level, consecutive enrolment is performed. Information bias will be minimized by the use of standard eCRF, questionnaire and physicians' training on the study protocol.

An additional limitation is that the physical functioning questionnaire (PF-10) is only assessing 10 items of the full 36-Item Short Form Health Survey (SF-36).

The 7-item satisfaction scale, which is to be completed by the patient in order to measure satisfaction with Spiolto® Respimat® use, is a self-designed Boehringer-Ingelheim scale, without a public source or validation status.

9.10 OTHER ASPECTS

9.10.1 Data quality assurance

A quality assurance audit/inspection of this study may be conducted by the sponsor or sponsor's designees or by IECs or by regulatory authorities. The quality assurance auditor will have access to all medical records, the investigator's study-related files and correspondence, and the informed consent documentation of this study.

9.10.2 Study records

Case Report Forms (CRFs) for individual patients will be provided by the sponsor via remote data capture. All of the clinical data and site/investigator characteristics will be captured via a web-based Electronic Data Capturing system. The site staff will enter and edit the data via a secure network, with secure access features (username, password and secure identification – an electronic password system). A complete electronic audit trail will be maintained.

Patients must not be identified on the eCRF by name. Appropriately coded identification (i.e. Patient numbers) must be used. All patient questionnaires will be paper-based and will be left at the site upon completion by the patient.

